11. TREATMENT SCHEDULE, DOSE ESCALATION, AND STOPPING RULES

11.1 Schedule for Subject Treatment

Subjects who satisfy all eligibility criteria will be enrolled into one of the following treatment cohorts:

Cohort #	Age Range (y)	Total Dose (vg/kg)	# Subjects
1	≥18	5.00E+12	2
2	≥18	1.00E+13	2
3	≥18	5.00E+13	2
4	≥18	1.20E+14	2
5	12-17	5.00E+13	2
6	12-17	TBD	2
7	5-11	TBD	2
8	5-11	TBD	2

Two subjects will be enrolled in each cohort, and will be dosed at least 4 weeks apart. SMC review occurs after at least 4 weeks of safety data is available from 2 subjects in each cohort.

The pediatric cohorts will be enrolled only after review of cumulative adult safety data by the SMC (see Section 12.3). The starting dose for pediatric cohorts 6 through 8 will be decided based on SMC review of study data, and must meet pre-defined safety criteria (see Pediatric Dosing).

Approximately 2 additional subjects may be added to any cohort after SMC review of study data if safety criteria are met (see Safety Monitoring Committee), with up to a total of 32 subjects in the study.

11.2 Dose Escalation Rules

Within each cohort, treatment will be staggered so that each subsequent subject will not be infused until the preceding subject has been observed for at least 4 weeks.

Dose escalation to the next cohort will not occur until at least 4 weeks after the last subject in the preceding cohort has been dosed and the safety data from the prior cohort has been reviewed by the SMC and the SMC has agreed to dose escalate.

Dosing and dose escalation will be paused if a Grade 3 or higher AE occurs, or if two Grade 2 AEs occur within the same organ class and persist for more than 2 weeks with therapy, provided these AEs are not related to the primary MPS II disease or treatment of the MPS II disease. In such an event, the SMC will be convened to assess for potential dose-limiting toxicity (DLT) and to provide recommendations on whether to expand the cohort at the same dose level, to dose deescalate, or to continue the study as planned (refer to the Stopping Rules).

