11.5 Study Stopping Rules

The safety data for all subjects within a cohort will be evaluated by the SMC at least 4 weeks after the last subject within that cohort was infused with SB-913. Safety data including AEs and clinical laboratory results (chemistry, hematology, etc.) will be evaluated to determine if it is safe to dose escalate. Subjects in the subsequent cohort may be screened and enrolled prior to the safety review

but will not be infused until the SMC has reviewed the data and approved the study for cohort escalation.

The SMC will also be convened to recommend whether the study should be stopped if any of the following criteria are met:

- Any one Grade 3 or higher AE, or any two Grade 2 AEs in the same system organ class that last more than 2 weeks with therapy, provided these AEs are not related to the primary MPS II disease or treatment of the MPS II disease.
- SAE not related to the primary MPS II disease.
- Death of a subject.
- Development of a malignancy.

The study may also be stopped for any of the following reasons:

- Sangamo, in consultation with the SMC or Regulatory Agency, decides for any reason that subject safety may be compromised by continuing the study.
- Sangamo decides to discontinue development of SB-913.

If stopping criteria are met, no further dosing of subjects will be performed until a substantial amendment is submitted to the regulatory authority(ies) for review, and the amendment has been approved by the site IRB/IEC or equivalent. When no further enrolling or dosing decisions are required of the SMC, the SMC will no longer meet. Sangamo will review subject safety data on an ongoing basis.

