12.3 Safety Monitoring Committee (SMC)

An external SMC with appropriate medical and scientific expertise will have oversight of the study.

The SMC will be convened after the completion of each cohort to advise whether it is safe to proceed with the next dose cohort and to provide recommendations on pediatric dosing and expansion of any cohort. The SMC may also be convened at any time if there are excessive or unexpected toxicities associated with the conduct of the protocol. Specifically, the SMC will be convened if the following occurs:

- Any one Grade 3 or higher AE, or any two Grade 2 AEs in the same system organ class that last more than 2 weeks with therapy, provided these AEs are not related to the primary MPS II disease or treatment of the MPS II disease.
- SAE not related to the primary MPS II disease.
- Death of a subject.
- Development of a malignancy.

The SMC will then evaluate all data to advise whether the changes should be made to the study or whether accrual and dosing should be halted. In addition, no further dosing of subjects will be performed until a substantial amendment is submitted to the regulatory authority(ies) for review, and the amendment has been approved by the site IRB/IEC or equivalent.

The SMC may also recommend changes to the enrollment of cohorts based on cumulative adult and pediatric safety and efficacy data from similar ongoing first-in-human clinical trials that are sponsored by Sangamo and that use *in vivo* rAAV2/6-based gene transfer of ZFNs. Specifically, study SB-318-1502 in MPS I subjects uses identical ZFNs components (SB-47171 and SB-47898) as the present study in combination with a different donor cDNA (encoding human alphaiduronidase) (Clinicaltrials.gov NCT02702115). Given the similarities of the approaches, relevant data from study SB-318-1502 and other trials sponsored by Sangamo may be shared with the SMC to expand the clinical experience, particularly as it relates to safety and dose, and such data can be used by the SMC to inform its recommendations for the present study.

When no further enrolling or dosing decisions are required of the SMC, the SMC will no longer meet. Sangamo will continue to review subject safety data on an ongoing basis.

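### The events that hold dosing are stated inconsistently: Section 11.2 and the synopsis escalation text give a shorter list with a wider exemption than Sections 11.5 and 12.3 and SAP Section 8

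*Protocol*

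**What the plan says.** **Protocol 11.2, repeated in the synopsis under Dose Escalation.** "Dosing and dose escalation will be paused if a Grade 3 or higher AE occurs", or when two Grade 2 AEs in one organ class last over 2 weeks on therapy. Both limbs apply "provided these AEs are not related to the primary MPS II disease or treatment of the MPS II disease". The SMC then meets and may recommend expanding the cohort, de-escalating, "or to continue the study as planned (refer to the Stopping Rules").

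**Protocol 11.5.** The same AE trigger with the same exemption, plus three more: an SAE unrelated to the primary disease, a death, and a malignancy. The consequence is explicit: "If stopping criteria are met, no further dosing of subjects will be performed until a substantial amendment is submitted" and the site's IRB/IEC (or equivalent) has approved it.

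**Protocol 12.3, repeated in SAP Section 8.** The same four triggers: the AE trigger, "SAE not related to the primary MPS II disease", "Death of a subject" and "Development of a malignancy". These convene the SMC, which advises on changes or a halt. A further sentence says that "no further dosing of subjects will be performed until a substantial amendment is submitted to the regulatory authority(ies) for review", again with IRB/IEC approval.

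**Synopsis, Safety Monitoring Committee and Stopping Rules.** The same added triggers, but they only convene the SMC. The synopsis does not mention a dosing hold pending an amendment.

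**The concern.** This is a first-in-human study with subjects dosed at least 4 weeks apart within a cohort. After each safety event someone must decide whether the next subject may be infused, and that decision should not depend on which section is open.

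Here it can. The lists differ in which events count, because SAE, death and malignancy are missing from 11.2. They differ in what is exempt: 11.2 exempts the disease and its treatment, the SAE trigger exempts the disease only, and death and malignancy exempt nothing. They also differ in what follows: a pause that the SMC can lift, a bar on dosing until an amendment is approved, or only a meeting.

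The treatment exemption matters in practice. Section 11.4 calls ERT the only approved therapy for MPS II, and subjects already on ERT continue it unless they enter ERT withdrawal. A reaction to ERT is therefore an event related to treatment of the disease.

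Two errors are possible. A subject could be infused while 11.5 requires a hold, or dosing could be stopped pending an amendment for an event that the 11.2 wording exempts.

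**Working it through.** The plan states no figure for this point, so the check is a logical comparison of the rules.

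**Inputs**
- Pause rule: Protocol 11.2.
- Halt list: Protocol 11.5, with the same triggers in 12.3 and SAP 8.
- Seriousness is separate from grade: under 10.1.4, hospitalization or its prolongation makes an event serious at any grade.
- Death is Grade 5 (10.3).
- ERT counts as treatment of MPS II (11.4).

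**Rules.** Let G be grade, P membership of a qualifying Grade 2 pair, S serious, D death, M malignancy, and A the attribution (disease, treatment or neither).
- 11.2 pause = (G ≥ 3 or P) and A = neither.
- 11.5 / 12.3 trigger = [(G ≥ 3 or P) and A = neither] or [S and A ≠ disease] or D or M.

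The first bracket of the second rule is the 11.2 rule itself. Every event that pauses dosing under 11.2 is therefore also on the 11.5 list, and disagreement can run in one direction only.

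**Results**

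| Event | 11.2 pause | 11.5 / 12.3 list |
|---|---|---|
| Serious, non-fatal, related to MPS II treatment, any grade | No | Yes |
| SAE below Grade 3, related to neither the disease nor its treatment, not in a qualifying Grade 2 pair | No | Yes |
| Death attributed to MPS II | No | Yes |
| Death attributed to MPS II treatment | No | Yes |
| Malignancy below Grade 3 and not in a qualifying pair | No | Yes |
| Malignancy of any grade attributed to MPS II or its treatment | No | Yes |
| Non-fatal SAE related to the disease, not a malignancy | No | No |
| Non-serious Grade 3 or higher AE related to MPS II treatment, not a malignancy | No | No |
| Grade 3 or higher AE related to neither | Yes | Yes |

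Grouping the two death rows and the two malignancy rows leaves four kinds of event on which the lists differ.

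**One event traced through.** A Grade 3 serious ERT reaction is exempt under 11.2 and under the first bullet of 11.5 and 12.3. The second bullet catches it, because that bullet exempts only the primary disease.

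**Consequences side by side**

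| Section | What a trigger leads to |
|---|---|
| 11.2 and synopsis Dose Escalation | Pause; the SMC may recommend continuing as planned |
| 11.5 | No further dosing until the amendment is submitted and approved |
| 12.3 and SAP 8 | SMC advises; same bar on dosing, automatic or following that advice depending on how the sentence is read |
| Synopsis SMC and Stopping Rules | SMC convened |

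The consequences thus conflict even for the trigger that every section shares. For an unrelated Grade 3 AE, 11.2 lets the SMC recommend carrying on, while 11.5 requires an approved amendment first.

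**The case against.** The strongest reply is that Section 11.2 ends by referring to the stopping rules, and 11.5 in the same chapter carries every added trigger with an express halt. The 11.2 list is a subset, so both sections can be obeyed together, and 11.2 nowhere says that dosing continues after an SAE or a death. This stands. A reader might infer that these events are not covered, or that 11.2 permits dosing after them; the documents do not support that, because silence in 11.2 is not permission.

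It does not dispose of the point. The reference to the stopping rules closes a sentence about what the SMC may recommend once an 11.2 trigger has been met, so it does not plainly add triggers. In the synopsis, the same reference leads to a stopping text that contains no hold pending an amendment.

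A second reply is that the narrower SAE exemption may be intended. It appears in the same form in 11.5, 12.3, the synopsis and SAP 8, and the treatment exemption still operates for non-serious events. This also stands. A reader might infer a drafting slip, but nothing in the documents shows one.

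Third, a reader might infer that 12.3 by itself halts dosing automatically. Its sentence follows the SMC's advice and can be read as depending on it. The automatic reading is clear only in 11.5.

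Finally, exclusion criterion 5 removes subjects with significant infusion reactions or anaphylaxis on idursulfase. Serious events also reach the sponsor within 24 hours, and moving to the next cohort needs SMC approval. These safeguards reduce the risk of error but do not settle which list applies.

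**Conclusion.** The concern holds as an inconsistency in lists, exemptions and consequences. It does not hold as a gap in coverage. Four kinds of event are outside the 11.2 and synopsis pause but halt dosing under 11.5, and no event goes the other way. For the shared trigger, the conditions for resuming dosing also differ.

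The documents give no basis for a frequency. They do not state the share of subjects on ERT or an expected rate of serious ERT reactions. A count of rule combinations would describe the wording and not how likely a conflict is.

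The conclusion assumes that ERT counts as treatment of MPS II, that seriousness is judged separately from grade, and that 11.5 is read literally. It should be corrected because the rule decides whether the next subject is infused.

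**What to change.** Reconcile Protocol 11.2, 11.5 and 12.3, the synopsis (Dose Escalation, Safety Monitoring Committee, Stopping Rules) and SAP Section 8. One list should state which events hold dosing and which exemptions apply to each trigger, and the other sections should refer to it without restating it. The same place should make clear whether the hold is automatic or follows SMC advice, and what must happen before dosing resumes. The content of the list, including whether any exemption is kept, is for the sponsor and the SMC to decide.

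The cost is a wording change to the protocol and the SAP. It needs no new data, assessments or subjects.

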11.3 Pediatric Dosing

Pediatric dosing will not be initiated until adult safety data has been obtained and reviewed by the SMC, and only after the following conditions have been met:

- ≥ 6 months of safety data from 2 adults treated with SB-913 at any dose; and
- \geq 4 weeks of safety data from 2 adults treated with SB-913 at the intended pediatric dose.

Younger pediatric subjects (Cohorts 7 and 8) will not be dosed until older pediatric subjects (Cohorts 5 and 6) have been dosed at the same dose level and \geq 4 weeks of safety data from each older subject has been reviewed by the SMC.

11.4 ERT Withdrawal

ERT using Elaprase (idursulfase) or equivalent is the only approved therapy for MPS II. ERT is beneficial but has significant drawbacks, which include the need for continuous life-long treatment; development of neutralizing antibodies; lack of efficacy in the brain (due to inability to cross the blood-brain barrier); continued cardiac, musculoskeletal, and upper airway complications; and the inconvenience and cost of weekly IV infusions (Tomanin et al, 2014).

The goal of SB-913 treatment is to abrogate or decrease the need for enzyme replacement therapy, by using engineered zinc finger nucleases (ZFNs) to site-specifically integrate a corrective copy of the enzyme iduronate-2-sulfatase (hIDS) transgene into the genome of the subject's own hepatocytes in vivo, resulting in life-long, liver-specific expression of IDS. Therefore, subjects who have received SB-913 may no longer require weekly administration of ERT, and may be considered for withdrawal of ERT (if applicable).

ERT withdrawal will be a controlled process with additional safety monitoring to reduce potential risk to the subject, and is an optional part of the study.

ERT withdrawal may be initiated by the Principal Investigator after consultation with the Sponsor, and only in subjects who are willing and who meet all of the following criteria:

- Are ≥ 12 weeks post-administration of SB-913.
- Are medically stable and can tolerate temporary discontinuation of ERT in the judgement of the Principal Investigator.
- Agree to additional safety monitoring and lab testing until ERT Withdrawal Follow-Up visit (see Appendix 2).

Study visits associated with ERT withdrawal may occur concurrently or independent of regular scheduled study visits, but should be combined with regular scheduled study visits whenever possible to reduce study burden. When combined, assessments associated with ERT withdrawal that are duplicated at the regular scheduled study visits should be waived (see Appendix 1). The ERT Withdrawal Follow-Up visit can occur at any time up to 12 weeks after ERT withdrawal at the discretion of the Principal Investigator.

ERT does not need to be restarted after the ERT Withdrawal Follow-Up visit. However, ERT may be re-initiated at any time based on clinical circumstances or at the judgement of the Principal Investigator.

ERT withdrawal may be repeated if previously unsuccessful. However, ERT withdrawal may not be attempted until at least 12 weeks after ERT has been resumed, and only at the discretion of the Principal Investigator and in consultation with the Sponsor. Subjects undergoing repeat ERT withdrawal must be willing and meet the criteria for initial ERT withdrawal listed above.

Documentation of dosing and administration of all ERT should be obtained and recorded on the ERT Administration Log.

11.5 Study Stopping Rules

The safety data for all subjects within a cohort will be evaluated by the SMC at least 4 weeks after the last subject within that cohort was infused with SB-913. Safety data including AEs and clinical laboratory results (chemistry, hematology, etc.) will be evaluated to determine if it is safe to dose escalate. Subjects in the subsequent cohort may be screened and enrolled prior to the safety review

but will not be infused until the SMC has reviewed the data and approved the study for cohort escalation.

The SMC will also be convened to recommend whether the study should be stopped if any of the following criteria are met:

- Any one Grade 3 or higher AE, or any two Grade 2 AEs in the same system organ class that last more than 2 weeks with therapy, provided these AEs are not related to the primary MPS II disease or treatment of the MPS II disease.
- SAE not related to the primary MPS II disease.
- Death of a subject.
- Development of a malignancy.

The study may also be stopped for any of the following reasons:

- Sangamo, in consultation with the SMC or Regulatory Agency, decides for any reason that subject safety may be compromised by continuing the study.
- Sangamo decides to discontinue development of SB-913.

If stopping criteria are met, no further dosing of subjects will be performed until a substantial amendment is submitted to the regulatory authority(ies) for review, and the amendment has been approved by the site IRB/IEC or equivalent. When no further enrolling or dosing decisions are required of the SMC, the SMC will no longer meet. Sangamo will review subject safety data on an ongoing basis.
12. SUBJECT WITHDRAWAL/DISCONTINUATION, AND SAFETY MONITORING COMMITTEE

12.1 Subject Withdrawal and Discontinuation from Study

Subjects may withdraw or should be discontinued from study for any of the following reasons:

- Request by the subject to withdraw.
- Request of Sangamo or primary care provider if he or she thinks the study is no longer in the best interest of the subject.
- Pregnancy prior to SB-913 infusion.
- Subject judged by the Principal Investigator to be at significant risk of failing to comply with the provisions of the protocol as to cause harm to self or seriously interfere with the validity of the study results.
- At the discretion of the IRB/IEC or equivalent, Office for Human Research (OHR), regulatory authority (e.g. FDA/MHRA or equivalent), Principal Investigator, or Sangamo.

Subjects will be strongly encouraged to continue and comply with follow-up safety evaluations. If a subject withdraws consent or discontinues from the study post-study treatment, a conference between the Principal Investigator and Medical Monitor will take place to ensure that the subject understands the importance of the study follow-up and that the study treatment cannot be reversed even if a subject drops out of the study follow-up. If the subject agrees, a reduced follow-up testing schedule may be arranged including telephone call and safety labs to assess treatment-related AEs and disease status.

12.2 Safety Monitoring and Mitigation Plan

The liver function (total and direct bilirubin, alkaline phosphatase, ALT, AST, LDH, albumin, and total protein) of study subjects will be monitored closely throughout the study as indicated above in Section 9.13.

Key potential anticipated risks are:

- Development of transaminitis due to cell-mediated immunity to the AAV capsid protein, the engineered ZFNs, or the endogenous hIDS; to minimize the potential immune response and to preserve hepatic function, prednisone or equivalent corticosteroid will be administered prophylactically starting 2 days prior to the SB-913 infusion and will be tapered over a period of approximately 20 weeks (see Appendix 3).
- Reduction in albumin synthesis; this is not expected given the small fraction (<1%) of transduced cells in which the albumin locus will be disrupted, and has not been observed in animal studies, in which levels of transduction and albumin locus disruption exceeded by several fold those expected in humans.
- Off-target modification at the SMCHD1 locus; this is not expected given that no off-target activity has been observed at clinically relevant levels of albumin on-target activity in human cells *in vitro* (see Section 8.1.2).

12.3 Safety Monitoring Committee (SMC)

An external SMC with appropriate medical and scientific expertise will have oversight of the study.

The SMC will be convened after the completion of each cohort to advise whether it is safe to proceed with the next dose cohort and to provide recommendations on pediatric dosing and expansion of any cohort. The SMC may also be convened at any time if there are excessive or unexpected toxicities associated with the conduct of the protocol. Specifically, the SMC will be convened if the following occurs:

- Any one Grade 3 or higher AE, or any two Grade 2 AEs in the same system organ class that last more than 2 weeks with therapy, provided these AEs are not related to the primary MPS II disease or treatment of the MPS II disease.
- SAE not related to the primary MPS II disease.
- Death of a subject.
- Development of a malignancy.

The SMC will then evaluate all data to advise whether the changes should be made to the study or whether accrual and dosing should be halted. In addition, no further dosing of subjects will be performed until a substantial amendment is submitted to the regulatory authority(ies) for review, and the amendment has been approved by the site IRB/IEC or equivalent.

The SMC may also recommend changes to the enrollment of cohorts based on cumulative adult and pediatric safety and efficacy data from similar ongoing first-in-human clinical trials that are sponsored by Sangamo and that use *in vivo* rAAV2/6-based gene transfer of ZFNs. Specifically, study SB-318-1502 in MPS I subjects uses identical ZFNs components (SB-47171 and SB-47898) as the present study in combination with a different donor cDNA (encoding human alphaiduronidase) (Clinicaltrials.gov NCT02702115). Given the similarities of the approaches, relevant data from study SB-318-1502 and other trials sponsored by Sangamo may be shared with the SMC to expand the clinical experience, particularly as it relates to safety and dose, and such data can be used by the SMC to inform its recommendations for the present study.

When no further enrolling or dosing decisions are required of the SMC, the SMC will no longer meet. Sangamo will continue to review subject safety data on an ongoing basis.

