9.32 ERT Administration Log

Frequency of ERT administration will be studied before and after administration of SB-913. Therefore, each dose of ERT given to the subject from the time of Screening will be recorded on the ERT Administration Log, including date and time of start and stop of ERT infusion. At each indicated visit, documentation of all ERT administration since the last visit must be obtained and confirmed. An assumed standing schedule (e.g., weekly) should not be used.

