#### 6.2 Secondary Endpoints and Analyses

Secondary endpoints will be summarized by presenting descriptive statistics of actual values and changes from baseline at each visit, where applicable. The secondary endpoints consist of the changes from baseline over time in the following assessments:

- IDS activity measured in plasma
- Assessments will be conducted at Screening, Baseline, Weeks 2, 4, 6, 8, 12, 16, 20, 24, 36, 48, Months 15, 18, 21, 24, 27, 30, 33, 36/End of Study (EOS), and at any Early Termination Visit. Total GAG, dermatan sulfate (DS) GAG, and heparin sulfate (HS) GAG levels measured in urine

At each sampling time point, the actual value and the change from baseline for IDS activity and urine GAG levels will be summarized using descriptive statistics and plotted over time by treatment cohort.

For subjects who undergo ERT withdrawal, changes from pre- to post- ERT withdrawal in the frequency and dose of ERT infusions will be evaluated and summarized using monthly, quarterly, and annualized total dose and number of infusions. Duration of ERT withdrawal may also be analyzed. The ERT withdrawal period is defined as the date recorded on the ERT Withdrawal Trigger CRF form to the first date after ERT withdrawal recorded on the ERT administration.

• AAV2/6 clearance measured by vector genomes in plasma, saliva, urine, stool, and semen by PCR

AAV2/6 clearance measured by vector genomes in the different samples will be plotted over time by treatment cohort.

CONFIDENTIAL Page 15 of 28

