#### 7.2.5 Adverse Event Summaries

For TEAEs, the following will be summarized and presented for the Safety Analysis Set overall and by dose cohort:

- i. An overall summary of TEAEs, which includes:
  - a. the number and percentage of subjects experiencing a TEAE
  - b. the number and percentage of subjects experiencing a TEAE equal to or greater than Grade 3 toxicity
  - c. the number and percentage of subjects experiencing a related TEAE
  - d. the number and percentage of subjects experiencing a TEAE leading to study withdrawal
  - e. the number and percentage of subjects experience a TEAE leading to death
  - f. the number and percentage of subjects experiencing a treatment emergent SAE (TESAE)
- ii. the number and percentage of subjects experiencing a TEAE by SOC and PT
- iii. the number and percentage of subjects experiencing a TEAE by SOC, PT and the highest toxicity grade
- iv. the number and percentage of subjects experiencing a TEAE by SOC, PT and the strongest relationship to study medication
- v. the number and percentage of subjects experiencing a TEAE by PT
- vi. the number and percentage of subjects experiencing a TEAE leading to study withdrawal by SOC and PT
- vii. the number and percentage of subjects experiencing a TESAE by SOC and PT

In the overall summary of TEAEs table (i), besides tabulating the number and percentage of subjects, the total number of TEAE episodes will also be provided. If a subject has repeated episodes of a particular TEAE, all episodes will be counted in the summary table.

In the remaining summary tables, the incidence of TEAEs will be calculated by dividing the number of subjects who have experienced the event by the total number of subjects in the Safety Analysis set. Thus, the incidence of TEAEs is shown in terms of the total number of subjects and not in terms of the total number of episodes. If a subject has repeated episodes of a particular TEAE, only the most severe episode, or the episode with the strongest causal relationship to study drug, will be counted in the summary tables.

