A subject with more than one type of TEAE in a particular SOC will be counted only once in the total of subjects experiencing TEAEs in that particular SOC. Since a subject could have more than one type of TEAE within a particular SOC, the sum of subjects experiencing different TEAEs within the SOC could appear larger than the total number of subjects experiencing TEAEs in that SOC. Similarly, a subject who has experienced a TEAE in more than one SOC will be counted only once in the total number of subjects experiencing AEs in all SOCs. At each level of summation (relationship, toxicity grade), subjects reporting more than one TEAE are

CONFIDENTIAL Page 18 of 28

counted only once using the strongest relationship to study medication and highest toxicity grade.

All AEs (serious and non serious) occurring after completion of the informed consent process and before the end of study, regardless of relationship to study drug, will be included and classified by SOC and PT using MedDRA in a listing by subject, grouped by dose cohort.

The listing will contain the following information: dose cohort, verbatim term, SOC, PT, severity, toxicity grade, relationship to study medication, date and day of onset, date and day of resolution, treatment given to treat the adverse event, the outcome, whether the event was an SAE, whether it led to withdrawal and whether it is a TEAE. Listings will be sorted by subject identification number, onset date, SOC, and PT. If the onset date is completely missing, then these events will be presented first. If the onset date is missing a month or a day, then these events will be presented before any complete dates.

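### A non-fatal, non-malignant Grade 3+ AE or SAE attributed to MPS II during study ERT withdrawal meets no mandatory SMC event trigger, and no planned AE output shows ERT status at onset

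*Protocol*

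**What the plan says.** **ERT withdrawal.** Protocol 11.4 makes it an optional part of the study from 12 weeks after SB-913. The investigator starts it after consulting the sponsor, in willing and stable subjects. No minimum length is set. On the one hand, "ERT does not need to be restarted after the ERT Withdrawal Follow-Up visit"; on the other, "ERT may be re-initiated at any time based on clinical circumstances".

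**SMC triggers.** Protocol 12.3 lists four events for which the committee must meet. The Synopsis, Protocol 11.5 and SAP 8 give the same list.
- One AE of Grade 3 or higher, or two persistent Grade 2 AEs in one organ class, "provided these AEs are not related to the primary MPS II disease or treatment of the MPS II disease".
- An "SAE not related to the primary MPS II disease".
- Death.
- Malignancy.

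The dosing pause in Protocol 11.2 carries the same exemption as the first trigger. No list has a trigger specific to ERT withdrawal.

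**AE outputs.** SAP 7.2.5 opens its table list with "For TEAEs, the following will be summarized and presented for the Safety Analysis Set overall and by dose cohort". The AE listing covers items such as "severity, toxicity grade, relationship to study medication, date and day of onset, date and day of resolution", but not ERT. Under SAP 7.2.3, relationship is recorded to the investigational drug only.

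**ERT data.** Protocol 9.32 states that "each dose of ERT given to the subject from the time of Screening will be recorded on the ERT Administration Log". SAP 6.2 gives the start of the off-ERT interval: "The ERT withdrawal period is defined as the date recorded on the ERT Withdrawal Trigger CRF form". It ends at the next recorded ERT date.

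**The concern.** Exempting background disease makes sense while standard care continues: ordinary MPS II progression should not halt a gene-transfer trial. The exemption fits less well once the study itself allows that care to stop. Serious worsening of MPS II is then what one would expect to see if the dose given does not replace ERT, and it is the kind of event that the wording removes from mandatory review.

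Restarting ERT protects the individual and needs no committee. But the SMC advises on escalation, expansion and pediatric dosing, and serious worsening off ERT bears on all three. In the safety tables, such an event would count as a TEAE with nothing to show that it began off ERT.

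**Working it through.** The plan gives no figure on this point, so the check is a reading of the triggers followed by timing arithmetic.

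**1. Trigger test** (Protocol 11.5 and 12.3, SAP 8), for a non-fatal, non-malignant event with onset off ERT:

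| Trigger | Attributed to MPS II | SAE attributed only to MPS II treatment |
|---|---|---|
| Grade 3+ AE or persistent Grade 2 pair | exempt | exempt |
| SAE | exempt | **met** |
| Death | not applicable | not applicable |
| Malignancy | not applicable | not applicable |

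An event attributed to MPS II meets 0 of 4 triggers. The SAE trigger exempts only the primary disease, so an SAE attributed solely to treatment still counts.

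**2. A cohort's own review.** Inputs: subjects dosed at least 4 weeks apart, review at least 4 weeks after the last dose (Protocol 11.2), withdrawal from Week 12 (11.4). At the minimum spacing:
- Two subjects: the review falls 8 and 4 weeks after their doses. Both are below 12, so it covers 0 withdrawal-eligible subject-weeks.
- Four subjects: it falls at 16, 12, 8 and 4 weeks. Eligible time is (16 − 12) + 0 + 0 + 0 = 4 subject-weeks.

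The next post-cohort review follows 8 weeks later if that cohort has two subjects, or 16 weeks later if it has four.

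**3. Eligible time before the final SMC review.** Assume that all N subjects are on ERT and are dosed one after another, subject i at week 4(i − 1), with the final review at week 4N. With follow-up F weeks, subject i contributes min(max(4N − 4(i − 1) − 12, 0), F − 12) eligible weeks before that review, out of F − 12. F is 156 (36 months) or 52 (exit to the long-term study at 12 months, Protocol 3.4).

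| N | F | Before final review | All eligible | Share |
|---|---|---|---|---|
| 16 | 156 | 52 + 48 + … + 4 = 364 | 16 × 144 = 2,304 | 15.8% |
| 16 | 52 | 3 × 40 + 220 = 340 | 16 × 40 = 640 | 53.1% |
| 32 | 156 | 116 + 112 + … + 4 = 1,740 | 32 × 144 = 4,608 | 37.8% |
| 32 | 52 | 19 × 40 + 220 = 980 | 32 × 40 = 1,280 | 76.6% |

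Here 220 = 40 + 36 + … + 4. Slower enrolment raises the shares and parallel cohorts lower them. Exit before 12 months, which Protocol 3.4 allows case by case, is not modelled.

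**4. Possible time off ERT per subject.** From 0 to (156 − 12)/156 = 92% of follow-up, or from 0 to (52 − 12)/52 = 77% with exit at Week 52. The plan narrows neither range.

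**5. Outputs.** None of the seven TEAE outputs in SAP 7.2.5 is split by ERT status, and no listing field carries it. The listing's withdrawal item does not supply it: the matching tables concern leaving the study.

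**The case against.** The strongest reply is that such events have several routes to the SMC.
- The wording that ties review content to one cohort (Protocol 11.2, 11.5) governs escalation. Expansion of any cohort and the doses for Cohorts 6 to 8 rest on the committee's review of study data (3.5, 11.1).
- Pediatric enrolment needs a review of cumulative adult data (3.5), and pediatric dosing needs at least 6 months of data from two adults (11.3). Taking 6 months as 26 weeks, that spans 2 × (26 − 12) = 28 withdrawal-eligible subject-weeks.
- Later post-cohort reviews may show the event, and the SMC may be convened at discretion (12.3).
- Eight monitoring visits (6.12), the ERT clinical assessment with the Medical Monitor (9.33) and 24-hour SAE reporting to the sponsor (10.4) protect the individual.

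All of this stands. A reader might infer that the SMC decides on expansion and children's doses without seeing off-ERT events; these sections do not support that. What remains is narrower: none of the SMC routes is prompted by the event, and the discretionary one is framed around excessive or unexpected toxicity, which expected disease worsening may not look like.

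A second reply is that the triggers lead to a dosing halt pending a substantial amendment, so exempting disease events is reasonable. That also stands, and it is why the fix should call for review only.

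A third is that no data are lost. ERT doses are in the log (9.32), and ERT is recorded as concomitant medication (7.2), which has a by-subject listing (SAP 5.6). With at most 32 subjects, cases can be matched by hand. This is correct: the gap is in planned presentation, not in collection. An on/off-ERT table would also compare self-selected, stable subject-time with the rest, so it is optional.

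**Conclusion.** The point holds in limited form. A Grade 3+ AE or SAE that is neither fatal nor malignant, is attributed to MPS II and starts during study ERT withdrawal meets no mandatory SMC event trigger. No planned AE table or listing shows that it started off ERT. That conclusion rests on the text alone and needs no assumption.

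The size is less certain. The 16% to 77% range assumes every subject is on ERT, although the inclusion criteria do not require it, and strictly sequential dosing at minimum spacing. A reader might take it as the proportion of events missed. It is only the share of withdrawal-eligible time that precedes the final SMC review, when the committee could still act; withdrawal is optional and the documents give no uptake or event rate. A reader might also infer that every SAE during withdrawal escapes the triggers, but one attributed only to MPS II treatment does not.

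Given the other routes and safeguards, this is an inexpensive improvement to patient safety rather than a flaw that undermines the trial.

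**What to change.** **Protocol 12.3 and SAP 8.** While the SMC is active, send it for review any Grade 3+ AE or SAE with onset between the ERT Withdrawal visit and ERT resumption, whatever its attribution to MPS II or its treatment. State that this rule alone invokes neither the pause in 11.2 nor the halt in 11.5 and 12.3, and that events meeting an existing trigger still follow the existing rules.

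**SAP 7.2.5.** Add an ERT-status-at-onset flag to the AE listing, based on the SAP 6.2 withdrawal period. Close that period at the last study visit if ERT is never restarted, and apply it to each period where withdrawal is repeated.

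**Optional.** Add a descriptive on/off-ERT summary of TEAEs, restricted to time after Week 12 in subjects on ERT at enrolment. Starting there keeps infusion events, the 2-to-9-week transaminitis window cited in Protocol 3.5 and the higher steroid doses out of the on-ERT side. The end of the steroid taper (to Week 19) remains in it.

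**Cost.** One paragraph in each document, a few extra SMC notifications and one field derived from data already collected. Once the SMC stops meeting, only the flag and the sponsor's ongoing review apply.
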